4.2.2 Secondary Objective

- To estimate the association between the sonographic score and the most recent (<5 years) computed tomography (CT) scan score (i.e., emphysema score).
- To estimate the association between the sonographic score and the patient's subjective severity of dyspnea (estimated by the mMRC scale).
- To estimate the association between the sonographic score and the patient's diffusion lung capacity (DLCO).
- To determine the sonographic components that are the most sensitive for the diagnosis of COPD.
- To assess the additive value of the patient's smoking status to the diagnostic accuracy of the sonographic score.

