4.8 Data to Capture

4.8.1 Required Data

We aim to collect the sonographic data as well as the PFT results for each participant. Furthermore, we plan to gather descriptive data from the medical records including –

1. Age -continuous variable. Values: above 18.
2. Gender - dichotomic variable (Female=1, Male=0).
3. BMI - continuous variable.
4. Smoking history (pack years)- continuous variable.
5. Comorbidities - nominal variable. Values: dichotomic variable (Yes=1, No=0)
6. Hypertension – ordinal variable. (0=Normal, 1=Elevated, 2= Stage 1, 3 = Stage 2, 4= Hypersensitive crisis). Values: 0=systolic<120 & diastolic<80, 1=systolic=120-129 & diastolic<80, 2=systolic=130-139 & diastolic 80-89, 3=systolic>140 & diastolic>90, 4= systolic>180 & diastolic>110.
7. Diabetes - dichotomic variable (Yes=1, No=0)
8. Other Lung diseases (such as cystic fibrosis, bronchiectasis, Interstitial lung disease, etc) - dichotomic variable (Yes=1, NO=0)
9. Ischemic Heart Disease - dichotomic variable (Yes=1, No=0)
10. Degree of dyspnea (based on the mMRC Dyspnea Scale) - ordinal variable (1=Grade 1 ,2= Grade 2, 3=Grade 3, 4 =Grade 4). See supplements for mMRC dyspnea scaling system.
11. Hemoglobin level (g%) - continuous variable.
12. Latest Venous/Arterial pH- continuous variable.
13. Latest Venous/Arterial HCO3- - continuous variable.
14. Latest Venous/Arterial pCO2- continuous variable.
15. Latest Arterial pO2 - continuous variable.
 - a. The blood attributes under investigation will be derived retrospectively from the electronic medical record of the current hospitalization, and blood tests will not be performed as part of this trial.
16. Past computed tomographic scans (most recent and up to 5 years prior) - ordinal variable (0= no emphysema (score 0),1= \leq 25% emphysema (score 1),2= \leq 50% emphysema (score 2), 3= \leq 75% emphysema (score 3),4= $>$ 75% emphysema (score 4)).

All required data for this study will be collected via electronic case report forms (eCRF).

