4.8.2 Data Collection

The final set of CRFs is designed to accommodate the specific features of the trial design. Modification of CRFs will only be made if deemed necessary by Soroka CRC. The CRFs will be filled out manually by the study personnel and or will be collected through the computer services database.

[figure not shown]
The following data will be collected:

- Demographic data: Age, Gender, BMI
- Detailed medical history, including smoking history, comorbidities, degree of dyspnea reported (based on mMRC score), and recent computed tomographic scan (up to 5 years prior).
- PFT results
- POCUS exam results

5 Statistical Considerations and Analysis Plan

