- To determine the sonographic components that are the most sensitive for the diagnosis of OLD - we can use a logistic regression analysis. The regression will provide estimates of the effect of each sonographic component on the probability of being diagnosed with OLD. In this analysis, we can use the sonographic components as predictor variables and OLD diagnosis as the outcome variable.
- To assess the additive value of the patient's smoking status to the sonographic score's diagnostic accuracy- will be based on a logistic regression analysis. In this analysis, we can use the sonographic score and smoking status as predictor variables and OLD diagnosis as

the outcome variable. The regression will provide estimates of the effect of each predictor on the probability of being diagnosed with OLD, as well as an estimate of the additional effect of smoking status beyond the sonographic score.

All statistical tests and/or confidence intervals, as appropriate, will be performed at $\alpha=0.05$ (2-sided) or $\alpha=0.025$ (1-sided), except for those specified otherwise. All p-values reported will be rounded to three decimal places. All statistical analyses will be conducted using SPSS 29.0 statistical software (IBM Corp Armonk, NY, USA).

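### The smoking objective asks for a gain in diagnostic accuracy, but section 5.2 names only regression effects and no accuracy comparison of score plus smoking against score alone.

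*Combined protocol and SAP*

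**What the plan says.** Section 4.2.2 (Secondary Objective) sets the target: "To assess the additive value of the patient's smoking status to the diagnostic accuracy of the sonographic score". The secondary analyses in section 5.2 (Statistical Analyses) repeat the target and name the method: "To assess the additive value of the patient's smoking status to the sonographic score's diagnostic accuracy- will be based on a logistic regression analysis". The model has the score and smoking status as predictors and OLD as the outcome.

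Section 5.2 then says what the model delivers. First, "The regression will provide estimates of the effect of each predictor on the probability of being diagnosed with OLD". Second, "an estimate of the additional effect of smoking status beyond the sonographic score".

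Sensitivity, specificity, PPV, NPV, the ROC curve, the AUC and two operating points (one at 80% sensitivity) appear in the primary analysis of section 5.2, where they describe the POCUS score alone.

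The one smoking variable defined in section 4.8.1 (Required Data) is item 4, "Smoking history (pack years)- continuous variable". Section 4.8.2 (Data Collection) mentions smoking history in general terms. Smoking status is not defined or coded anywhere.

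**The concern.** The objective concerns accuracy, while the named outputs concern association. An adjusted odds ratio for smoking says how the odds of OLD differ between patients with the same score. It does not say how much better the score separates patients with and without OLD once smoking is known.

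If only the odds ratio is reported, a clear effect may be read as a worthwhile improvement of the test. The improvement could be modest or very small, depending on how well the score already discriminates and how common smoking is. An analyst who follows section 5.2 to the letter has no figure that answers the declared objective.

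**Working it through.** The plan states no figure for this objective, so there is none to reproduce. The check has three steps.

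**1. Target against output.**

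| | Target (4.2.2, repeated in 5.2) | Outputs named in 5.2 |
|---|---|---|
| Quantity | Gain in diagnostic accuracy over the score | Effect of each predictor on the probability of OLD; additional effect of smoking |
| Scale | AUC, sensitivity, specificity | Regression coefficient or odds ratio |
| Comparison | Score plus smoking against score alone | None named |

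**2. Does the odds ratio fix the gain?** The documents give no prevalence of OLD or of smoking, so these inputs are assumptions: 40% OLD, 40% smokers among patients without OLD, binary smoking independent of the score given OLD status, and a score that is normal with unit variance and mean 0 without OLD, μ with OLD.

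- Score alone: AUC = Φ(z), with z = μ/√2.
- Score plus smoking: the best combination is μ × score + ln(OR) × smoking. Let p0 and p1 be the smoking proportions without and with OLD, and d = ln(OR)/(μ√2). Then AUC = a·Φ(z + d) + c·Φ(z) + b·Φ(z − d), with a = p1(1 − p0), b = (1 − p1)p0 and c = 1 − a − b.
- The proportion with OLD drops out of this formula.

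For OR = 2 and p0 = 0.40, the smoking odds with OLD are 2 × 0.40/0.60 = 1.333. So p1 = 0.571, a = 0.343, b = 0.171 and c = 0.486.

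- Score AUC 0.70: z = 0.524, μ = 0.742, d = 0.693/1.049 = 0.661. AUC = 0.343 × 0.882 + 0.486 × 0.700 + 0.171 × 0.446 = 0.719, a gain of 0.019.
- Score AUC 0.89: z = 1.227, μ = 1.735, d = 0.693/2.453 = 0.283. AUC = 0.343 × 0.934 + 0.486 × 0.890 + 0.171 × 0.827 = 0.8945, a gain of 0.0045.

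Simulation with a rounded 0–10 score and 400,000 patients per scenario agrees:

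| Odds ratio | Low score AUC | Middle | High |
|---|---|---|---|
| 2 | 0.696 to 0.716 | 0.795 to 0.806 | 0.895 to 0.900 |
| 3 | 0.695 to 0.741 | 0.795 to 0.820 | 0.896 to 0.907 |

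Over a wider range (score AUC 0.64 to 0.92, 10% or 50% smokers among patients without OLD), an odds ratio of 2 goes with gains from 0.002 to 0.029, and an odds ratio of 3 with gains from 0.004 to 0.059. One odds ratio is thus compatible with gains that differ more than tenfold.

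**3. Which accuracy comparison works at N = 200?** Trials of 200 patients were simulated with the 40%/40% assumptions and score AUCs of about 0.70, 0.79 and 0.89. The ranges cover separate simulation runs.

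- No smoking effect: the apparent AUC gain, with models fitted and assessed in the same patients, was above zero in about 85% to 93% of trials. Uncorrected, it is biased upwards.
- No smoking effect, paired DeLong test: it found a gain in only 0.2% to 1.9% of trials, against a nominal 2.5% in that direction.
- True odds ratio of 2: the DeLong test detected a gain in about 8% to 11% of trials, and the test of the regression term in about 41% to 61%.

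The regression term is therefore the better test. The AUC difference is needed for size, and only after correction for optimism.

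**The case against.** The strongest case for the plan is that it leaves the accuracy step unstated without excluding it. Section 5.2 says that the assessment rests on a logistic regression and does not make the effects the sole output. The same fitted model yields predicted probabilities, to which the ROC methods of the primary analysis could be applied. The smoking term is also relevant, since it tests whether smoking carries information beyond the score. Both points stand. They make the repair cheap, but they do not prespecify an accuracy measure, so the gap remains.

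A reader might go further and infer that smoking status cannot be analysed because only pack-years are collected. The documents do not support that. Pack-years can be used as they are, or split into ever and never at zero. Section 4.8.2 lists smoking history without limiting it to pack-years, and no text says that status means never, former and current. An accuracy gain can be computed from pack-years. What remains is a definition gap: the plan does not say which form enters the model.

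The illustration uses binary smoking and says nothing about the gain from continuous pack-years. Nor does it show that the gain is always negligible: at an odds ratio of 3 and a score AUC of about 0.70, it is close to 0.05.

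**Conclusion.** The concern holds for the output. The plan declares an accuracy objective and names only regression effects for it, so the size of the accuracy gain is not prespecified. Under the stated assumptions, an odds ratio of 2 corresponds to an AUC gain of about 0.02 at a score AUC of 0.70 and about 0.005 at 0.89. The exact values depend on those assumptions. The conclusion that an odds ratio does not fix the gain does not depend on any one of them.

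A reader might infer that the regression is the wrong analysis and should give way to a comparison of AUCs. That is not supported: the regression term is a valid test and, at N = 200, much more powerful than a DeLong comparison. What is missing is a measure of size. This is one of five secondary objectives, and neither the primary analysis nor the sample size depends on it.

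**What to change.** In the secondary analyses of section 5.2:

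- Keep the Wald or likelihood-ratio test of the smoking term, adjusted for the score, for inference, and report the odds ratio with its 95% CI.
- Define the added value as the AUC of the score-plus-smoking model minus the AUC of the score alone, in the same patients. Correct it for optimism by bootstrap: refit in each resample, take the gain there minus the gain of those refitted models in the original data, average, and subtract the average from the apparent gain. Give a bootstrap 95% CI.
- Optionally, add the change in specificity at the planned 80% sensitivity point.
- Do not apply a DeLong test to these nested models.
- As a minor point, state that the smoking predictor is pack-years as collected in section 4.8.1, or ever/never derived from it, and fix the choice before the data are analysed.

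The cost is a few sentences and some extra analysis of data already planned, with no new model. The reported gain may look smaller than the odds ratio suggests.

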5.3 Primary Endpoints

Our primary endpoint is to diagnose OLD with POCUS examination (compared to the PFT which is considered the gold standard).

6 Adverse Events

There are no known adverse events to the point-of-care ultrasound exam.

6.1 Adverse Event Definition

6.1.1 Adverse Event

Any undesirable experience (sign, symptom, illness, abnormal laboratory value, or other medical events) occurring to a subject, that is considered related to the investigational treatment regimen prescribed as part of the clinical protocol, predefined in the clinical protocol, and/or Instructions For Use, that is identified or worsens during a clinical study.

6.1.2 Treatment-related Adverse Event

A treatment-related adverse event is defined as any adverse event, for which a causal relationship between the treatment and the event is at least a reasonable possibility, i.e., the relationship cannot be excluded.

6.1.3 Serious Adverse Event

A serious adverse event is considered one of the following: Death, Life-threatening, Hospitalization (initial or prolonged), Disability - significant, persistent, or permanent change, impairment, damage or disruption in the patient's body function/ structure, physical activities, or quality of life, Congenital anomaly or requires intervention to prevent permanent impairment or damage.

In the event of a serious adverse event, the investigational site must inform the EC up to 48 hours after becoming aware of the event. An initial written report will be provided to the EC within 2 working days after the investigator learns of an unanticipated adverse treatment effect. All unanticipated adverse effects are to be reported throughout the entire time that the patient remains active in the study.

6.2 Intensity of Adverse Event

The following categories of the intensity of an adverse event are to be used:

- Mild: Awareness of a sign or symptom that does not interfere with the subject's usual activity or is transient, resolved without treatment, and with no sequelae;
- Moderate: Interferes with the subject's usual activity, but the subject is still able to function.
- Severe: Events that interrupt a subject's usual daily activity and generally require a systemic device therapy or other treatment.

6.3 Anticipated Adverse Event

In this study, we do not anticipate adverse events.

6.4 Outcome

The clinical outcome of the event at the time of the last observation will be characterized as follows:

1. Not Recovered/Not Resolved
2. Recovered/Resolved
3. Recovered/Resolved with Sequelae
4. Recovering/Resolving
5. Fatal
6. Unknown

6.5 Treatment or Action Taken

The Principal Investigator will decide whether the subject needs any additional treatment or withdraw the subject from the study. In any case of detection of any cardiac or lung abnormality, a formal notification- verbal as well as written will be placed. The notification of any abnormal finding will be transferred to the pulmonologist as well as to the medical team from the referral unit.

6.6 Documentation

All adverse events, from signing the informed consent until EOS, whether observed directly or reported by the patient, will be collected and recorded. Non-serious adverse reactions or events are not required to be reported in an expedited manner but will be recorded on the data collection forms.

Serious Adverse events must be listed on the appropriate CRF. All SAEs will be characterized by the following criteria:

1. Relatedness
2. Outcome
3. Treatment or action taken.

All SAEs must be recorded on the SAE Form within 48 hours of the research staff becoming aware of the event.

For each SAE, the following information will be collected: full details in medical terms with a diagnosis, if possible, its duration (start and end dates; times, if applicable), action taken, outcome and causality in the opinion of the investigator (must be made by a doctor).

6.7 Expedited Reporting of Serious Adverse Events

The procedure for reporting any Serious Adverse Event is as follows:

1. Report any serious adverse event to the EC according to the investigational site's EC procedures.
2. Complete appropriate Event Form(s) for any complication and/or serious adverse events.
3. Submit physician/nurse notes or discharge summaries related to the reported event, as requested.

4. Report of a subject death must be along with a brief statement of the pertinent details, and the death records/certificate or autopsy report, if available/Performed.

Clear pathways have been developed for the reporting and analysis of serious adverse events. Study site personnel are responsible for SAE identification. SAEs are reported by the site to the local EC, the sponsor within 48 hours of becoming aware of the event.

7 Ethical and Regulatory Considerations

8 Subject Confidentiality

Subject confidentiality will be maintained throughout the study in a way that assures that data can always be tracked back to the source data. For this purpose, a unique subject identification code will be used that allows the identification of all data reported for each subject.

Data relating to the study might be made available to third parties (for example in case of an audit performed by regulatory authorities) provided the data are treated confidentially and that the subject's privacy is guaranteed.

8.1 Sources of Materials

No tissue or any other physical specimen will be taken from the patients.

All of the data obtained for this study will be obtained prospectively.

Copies of data obtained as part of the study will be retained by the clinical research center, with appropriate source documentation, on all subjects that sign informed consent. The data utilized in this study are described above and consist of information from medical records or study-specified measures and interventions.

8.2 Maintaining Records

The principal investigator will maintain copies of all study-related correspondence, regulatory documents, data, shipment of supplement accountability logs, adverse supplement effects and

other records related to the clinical study. The principal investigator will maintain records related to the signed Investigator Agreements.

8.3 Site Record Retention Policy

All core laboratories and clinical sites will maintain study records until the principal investigator notifies them and the reviewing regulatory authorities that research is completed or terminated under the clinical investigation in compliance with national law. Record retention dates will be provided to study sites by the principal investigator at the onsite closeout visit.

8.4 Informed Consent and Ethics Committee

All subjects must provide written informed consent in accordance with the local clinical site's EC. A signed Informed Consent must be obtained from each subject prior to commencing screening/baseline evaluations. One copy of the Informed Consent document will be given to the subject and another retained by the Investigator.

